Should any of the participants decide to withdraw from the study voluntarily or request self-discharge, another patient will be added to the study until 20 patients have reached conclusion either by medical discharge or death within a 20-day hospitalization follow-up. Patient data will be used up to the date of voluntary withdrawal or self-discharge.

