4.1 Study design

This is a single-arm, open-label, phase II clinical trial to evaluate the safety and efficacy of thymic peptides in the treatment of hospitalized COVID-19 patients in Honduras, at the Hospital de Santa Bárbara Integrado. A participant-level comparison will be made based on registry data of the Hospital de Santa Bárbara Integrado, after propensity score matching.

In total, 20 patients will be recruited from the designated hospital for COVID-19 patient care, including those who have signed informed consent and who meet the inclusion criteria. For the generation of the comparison group through data from clinical records, it will be carried out by authorization from the Hospital de Santa Bárbara Integrado, given its retrospective nature, without experimental intervention.

Clinical characterization

Once the protocol is started, the information corresponding to the general data, signs, symptoms, physical examination and laboratory values of each patient will be recorded daily in the data collection instrument. The record will be made on paper, which will be digitized and sent under encryption to the principal investigators every day.

As a quantitative method, the following laboratory findings will be considered to evaluate clinical progress, according to the requirement and availability of the hospital:

- Complete blood count
- C-reactive protein
- D-dimer
- Ferritin
- Procalcitonin
- Lactate
- AST

- ALT
- BUN
- Creatinine

Administration of thymic peptides (Unicahsina)

Thymic peptides (Unicahsina) will be administered in an oral dose of 250 mg per day. In the intubated patient, the administration will be done through a nasogastric tube. The presentation of thymic peptides (Unicahsina) will be in lyophilized form, which will be diluted in 50 ml of drinking water prior to administration. It should be administered on an empty stomach one hour before or two hours after a meal. If the patient is discharged, or if they need to be referred to an ICU, all the information will be gathered up to that moment and the administration of Unicahsina will be stopped.

Primary outcome measures

1) Time to participant recovery [Time Frame: During hospitalization for up to 20 days.]

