Measured in days to clinical recovery that will be defined as the first day, during the 20 days after enrollment, on which a patient met the criteria for category 1, 2, or 3 on the eight-category ordinal scale. The categories are as follows: 1, not hospitalized and no limitations of activities; 2, not hospitalized, with limitation of activities, home oxygen requirement, or both; 3, hospitalized, not requiring supplemental oxygen and no longer requiring ongoing medical care; 4, hospitalized, not requiring supplemental oxygen but requiring ongoing medical care (related to Covid-19 or to other medical conditions); 5, hospitalized, requiring any supplemental oxygen; 6, hospitalized, requiring noninvasive ventilation or use of high-flow oxygen devices; 7, hospitalized, receiving invasive mechanical ventilation or extracorporeal membrane oxygenation (ECMO); and 8, death.

2) Number of participants with treatment related adverse events as assessed by the Common Terminology Criteria for Adverse Events Version 5.0 (CTCAE v5.0) [Time Frame: Up to 20 days]

Number of participants who experience adverse events \geq Grade 3, as defined by the CTCAE v5.0.

3) Number of participants with treatment related side effects as assessed by the General Assessment of Side Effects (GASE) [Time Frame: Up to 20 days]

Number of participants who experience severe side effects as defined by the GASE.

Secondary Outcomes measures

1) Overall survival defined as the time from the start of treatment until death due to any reason [Time Frame: Up to 20 days]

Time for overall survival will be measured in days.

Other complementary analyzes

Computerized axial tomography and chest radiography

A Computerized tomography without contrast will be performed, with the patient in the supine position and the image acquisition will be carried out at the end of inspiration. The following parameters will be requested to obtain axial images: 1.25 mm thick, 1.25 mm interval, 120 kVp. If it is possible, chest radiographs will be requested in posteroanterior projection. However, in patients whose clinical condition warrants it, anteroposterior radiography will be considered. The images will be obtained at the moment of maximum inspiration, either with instruction to the patient or by controlling the ventilator console in the case of intubated patients.

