All quantitative data will be described using parameters such as the mean \pm standard deviation, or as the median (minimum and maximum). Qualitative data will be described by the number of cases (proportion%). Patient characteristics will be compared using the chi-square test or Fisher's exact test for categorical data. For continuous variable data, the Wilcoxon test or Student's t test will be employed. The analysis of time to a particular event will be carried out using the Kaplan-Meier method, and the analysis of differences between groups will be calculated with the log-rank test. The Cox proportional-hazard model will be used to estimate the hazard ratio and 95% confidence interval (CI). Propensity score matching methodology will be used to generate the comparison group from the clinical records. A p-value less than 0.05 will be required to establish significance. All analyses will be performed using SPSS and GraphPad Prism software.

SECTION 5 - ANONYMITY AND CONFIDENTIALITY OF DATA

The data will be obtained from the healthcare center assigned to treat positive cases of COVID-19, through the clinical record designed as an instrument for this study. The laboratory and imaging test reports, as well as the clinical records, will be digitized and sent to the principal investigators using the SOPHOS encryption software. This last part will ensure the confidentiality of each patient's data between devices while transferred. Access will be given to the Dirección General de Vigilancia del Marco Normativo de la Secretaría de Salud de Honduras (General Directorate for Regulatory Framework Surveillance of the Ministry of Health of Honduras) for the monitoring of the study. The hospital will have a password-protected electronic device. The access will be limited exclusively to medical doctors assigned for the study.

The physical documents will be attached to the patient clinical file at the end of the hospitalization.

For the data produced by CT or chest x-ray, the HOROS software will be used to visualize and anonymized DICOM files before sending them to radiologists. The confidentiality in transferring this information will be ensured by using the SOPHOS software.

SECTION 6 - POTENTIAL RISKS AND BENEFITS

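### Read literally, stopping information at ICU referral or discharge leaves 20-day survival, and for ICU referrals also recovery, without the data they need

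*Combined protocol and SAP*

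**What the plan says.** All references are to Version B.

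- **Stop rule** (section 4.1, Administration of thymic peptides): "If the patient is discharged, or if they need to be referred to an ICU, all the information will be gathered up to that moment". The rest of the sentence ends dosing at the same point.
- **Survival, the only secondary outcome** (section 4.1): "Overall survival defined as the time from the start of treatment until death due to any reason [Time Frame: Up to 20 days".
- **Recovery, the first primary outcome** (section 4.1): "the first day, during the 20 days after enrollment, on which a patient met the criteria for category 1, 2, or 3" on the eight-category scale. Categories 1 and 2 are the non-hospitalized states. The stated time frame is the hospital stay, capped at 20 days.
- **Completion** (section 2.2): recruitment continues "until 20 patients have reached conclusion either by medical discharge or death within a 20-day hospitalization follow-up". Only patients who withdraw or discharge themselves are replaced, and for them "Patient data will be used up to the date of voluntary withdrawal or self-discharge".
- **Data source** (section 5): "The data will be obtained from the healthcare center assigned to treat positive cases of COVID-19", and "The physical documents will be attached to the patient clinical file at the end of the hospitalization".
- **Analysis** (Statistical Analysis Plan): "The analysis of time to a particular event will be carried out using the Kaplan-Meier method", with a log-rank test and a Cox model. No censoring rule is given for ICU referral, discharge or death before recovery.

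**The concern.** The stop rule has two parts: one ends the drug and the other ends the information. Ending the drug is a treatment decision. Ending the information cuts follow-up short of the window that the endpoints use. A patient referred to an ICU on day 5 may die or recover on day 12, and under the literal rule neither event is recorded. A patient discharged on day 8 may die on day 15, and that death is not recorded either.

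ICU referral marks deterioration. If referred patients are censored at that point, the Kaplan-Meier and Cox methods assume that they carry the same later risk as those still on the ward, which is implausible. The affected outcomes are a primary endpoint and the only secondary endpoint, in a treated group of 20 where each patient counts for 5 percentage points.

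**Working it through.** The plan gives no event rate, referral rate or power calculation, so there is no figure of its own to reproduce. The check has three parts: a comparison of the texts, a bound that needs only the sample size, and an illustration on assumed counts.

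**1. The texts side by side**

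| Event | Survival to day 20 | Recovery within 20 days | Completion rule (2.2) |
|---|---|---|---|
| ICU referral | Later deaths not recorded: conflict | Later recoveries not recorded: conflict | Not listed as a conclusion: inconsistent with the stop rule |
| Discharge | Later deaths not recorded: conflict | Already category 1 or 2: no conflict | Medical discharge is a conclusion: agrees with the stop rule |

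Section 2.2 therefore points to continued follow-up after ICU referral, but not after discharge. No other section describes outcome collection after either event.

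**2. Bound for referred patients**

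Input: n = 20 treated (section 2.1). The number referred, k, is not in the documents and is assumed. If the fate of k patients is unknown, 20-day mortality is undetermined by up to k/20:

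- k = 1: 1/20 = 5 points
- k = 2: 2/20 = 10 points
- k = 4: 4/20 = 20 points

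This counts the referred patients only. Patients discharged before day 20 add to it.

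**3. Illustration for mortality**

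Assumed: k = 4 referred on day 5, one ward death on day 8, no deaths after discharge. Let m be the number of referred patients who die by day 20, and d the number discharged before day 8.

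- Full follow-up: (1 + m)/20 = 5%, 10%, 15%, 20%, 25% for m = 0, 1, 2, 3, 4.
- Kaplan-Meier with the ICU cut alone: 1/(20 − 4) = 1/16 = 6.3%.
- Kaplan-Meier with both cuts: 1/(20 − 4 − d). For d = 5, 1/11 = 9.1%. For d = 8, 1/8 = 12.5%.

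The ICU cut alone gives too low a mortality as soon as one referred patient dies. With both cuts and d = 8, the 12.5% is too high for m = 0 or 1 and too low for m = 2 or more, because early discharges shrink the risk set and the single ward death weighs more. So the sign of the error is not fixed even within the treated group.

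**4. Illustration for recovery**

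Assumed: the same 4 referred on day 5, before any recovery; the ward death kept as not recovered; the other 15 ward patients all recover.

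- Referred patients censored: 15/16 = 93.8%.
- Referred patients followed: from 15/20 = 75% (none recovers) to 19/20 = 95% (all four recover).

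If three of the four recover, the true figure is 18/20 = 90%, so censoring overstates recovery unless all four recover. For k = 2 and 17 ward recoveries, the figures are 17/18 = 94.4% censored, against 17/20 = 85% to 19/20 = 95% followed. The plan does not say that referred patients would be censored. Keeping them as not recovered would give 75% for k = 4, which is right only if none of them recovers.

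**The case against.** The strongest reply is that the sentence stands under drug administration and ends by stopping the drug, so it may only close the dosing record. Section 2.2 supports this for ICU referral: a referred patient has not concluded, which implies continued follow-up. Section 5 files the study documents when the hospital stay ends, not at referral, which would fit recording through an ICU stay in the same hospital. The documents do not say whether the hospital has its own ICU or whether referral means transfer elsewhere.

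This reply has weight, but it does not settle the matter. The sentence refers to all the information, not to dosing data. Section 2.2 uses similar wording as a true data cut for withdrawals. On discharge, section 2.2 gives no help, since medical discharge ends participation there.

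A reader might infer that outcomes are lost for everyone who deteriorates. The documents do not support that. Intubated patients may be dosed by nasogastric tube, section 6.1 provides for continuing treatment when intubation is needed, imaging of ventilated patients is planned, and category 7 of the scale covers invasive ventilation. Only patients actually referred to an ICU are affected and, for survival, those discharged before day 20.

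A reader might also infer that the rule favours the product over the registry controls. That would need controls to be followed further than treated patients. Controls come from retrospective records of the same hospital, and their follow-up after referral or discharge is not described. If both groups are cut alike and have the same true outcomes, the comparison shows no difference.

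**Conclusion.** The concern holds, conditionally. Followed as written, the stop rule prevents measurement of 20-day all-cause survival after ICU referral or discharge, and of recovery after ICU referral. It does not harm recovery through discharge. It is also inconsistent with the completion rule for referred patients.

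The firm part of the size is the bound: up to k/20 of 20-day mortality undetermined by referred patients, 5 points for each, with k unknown. The other percentages rest on assumed referral, death and discharge counts and show only how the error behaves. Censoring at referral would be informative, but the direction of any bias in the matched comparison cannot be stated from the documents. If follow-up to day 20 was always intended, the defect is one of wording plus a missing censoring rule. If it was not, the endpoints cannot be measured as defined for these patients. Either way the change should be made, since it is cheap and touches a primary endpoint.

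**What to change.** 1. Amend the sentence under Administration of thymic peptides so that ICU referral or discharge stops dosing but not outcome collection.
2. Record vital status to day 20 for every treated participant, and ordinal category to day 20 for those referred to an ICU, by record request or call.
3. State in the Statistical Analysis Plan that deaths after referral or discharge count as events in the 20-day survival estimate, that ICU referral is not a censoring event, and that patients who die before recovery stay in the recovery analysis as not recovered through day 20.
4. For the matched comparison, apply one ascertainment rule to both groups. If control vital status after discharge cannot be obtained, use hospital records, including ICU records, to day 20 in both. Calling treated patients while controls are known only from records would create the imbalance that the rule is meant to avoid.

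Cost: one amended sentence, a short addition to the analysis plan, and a few record requests or calls. Sample size and treatment do not change. The drawback is that deaths after discharge may be usable only in the treated-arm estimate. The Summary of Changes reports the length-of-stay analysis in the past tense, so data collection may be over. In that case the follow-up data would have to be retrieved retrospectively.

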2.3 Criteria

Inclusion Criteria:

- 1. Confirmed case of COVID-19 by viral nucleic acid (RNA) detection, viral antigen detection, or detection of antibodies to the virus.
- 2. Participants that require hospitalization under Honduran Ministry of Health Guidelines for Clinical Management of COVID-19 Adult Patients: Stage IIb, defined as a patient with or without risk factors that presents with warning signs (shortness of breath, tachypnea), and altered inflammatory parameters.
- 3. Participants that present with at least one of the following: oxygen saturation level below 94 percent; complete blood count showing lymphopenia, neutrophilia, or both; positive C-reactive protein; chest radiography or CT scan with ground-glass opacities.
- 4. Male or female at least 21 years old.

Exclusion criteria

- 1. COVID-19 patients that do not require hospitalization under Honduran Ministry of Health Guidelines for Clinical Management of COVID-19 Adult Patients: phase IA (asymptomatic), phase IB (mild symptoms without risk factors), or phase IC (mild symptoms with risk factors).
- 2. Participants currently in other clinical trials evaluating experimental drugs.
- 3. Known history of allergic reactions to thymic peptides or calf thymus acid lysate derivatives.
- 4. Organ transplant recipients.
- 5. Women who are pregnant or breast feeding.

SECTION 3. PARTICIPANT RECRUITMENT

Patients who meet the inclusion criteria and are hospitalized in Honduran facilities designated for the care of patients with COVID-19, will be recruited. Patients over 20 years of age capable of giving their consent will be included. In case that the patient is unable to authorize participation, authorization will be requested from his legal representative.

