Prior to their incorporation into the study, patients will be approached by the specialist or health personnel present on behalf of the Medical Research Group of the Catholic University of Honduras. In addition, there will be auxiliary methods with electronic devices that will allow telemedicine to be carried out between the principal investigators of the study and the potential participants. This last procedure will be carried out with encrypted methods that guarantee the confidentiality and anonymity of the patients. The purpose and procedures of the investigation will be explained, as well as clarifying any doubts that may arise. Once consent has been obtained, the clinical data registration will begin, and the application of the protocol will be coordinated with the treating physicians.

SECTION 4 - METHODOLOGY AND PROCEDURES

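### Registry controls have no day 0 and no at-risk rule, so the matched log-rank/Cox comparison can be biased in either direction if participants enroll after their admission day

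*Combined protocol and SAP*

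**What the plan says.** All references are to Version B of the combined protocol and SAP.

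- **Primary outcome 1 (Section 4.1).** Recovery is "defined as the first day, during the 20 days after enrollment, on which a patient met the criteria for category 1, 2, or 3" of an eight-category ordinal scale. The time frame is "During hospitalization for up to 20 days".
- **Secondary outcome (Section 4.1).** Overall survival is "the time from the start of treatment until death due to any reason".
- **Comparison group (Section 4.1, Study design).** Controls are taken from the same hospital's records, "given its retrospective nature, without experimental intervention".
- **Statistical Analysis Plan.** "Propensity score matching methodology will be used to generate the comparison group from the clinical records". Groups are compared by Kaplan-Meier and log-rank, with a Cox hazard ratio, at p < 0.05.
- **Recruitment (Section 3).** Eligible patients who "are hospitalized in Honduran facilities designated for the care of patients with COVID-19, will be recruited". "Once consent has been obtained, the clinical data registration will begin".
- **Replacement rule (Section 2.2).** Participants conclude by medical discharge or "death within a 20-day hospitalization follow-up".

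There is no other text on how controls are dated, selected in time or scored. Version A has the same gap.

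**The concern.** Both day-0 definitions rest on events that happen only to participants: enrollment and first study dose. Neither can be applied to a patient found in old records, so whoever runs the analysis must choose a starting day for controls. The charts are retrospective, so that choice can be made after the outcomes are known.

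Participants must also still be in hospital, alive and unrecovered when they enroll. Nothing requires this of controls on any given day. Propensity matching on patient characteristics balances those characteristics; it does not put the two groups on the same hospital day.

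At stake is the only between-group efficacy analysis that the SAP describes, in a trial whose general objective is to demonstrate efficacy as well as safety. The CTCAE and GASE counts and the participant-only descriptions are unaffected.

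**Working it through.** **Inputs from the documents.** 20 participants; a 20-day window; log-rank and Cox; p < 0.05 (sidedness not stated, so two-sided is assumed, 2.5% per side). The plan gives no power, effect size or matching ratio, so it has no figure of its own to reproduce.

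**Inputs assumed.** Matching 1:1; enrollment L = 1, 2 or 3 days after admission; Weibull time from admission to recovery with shape k and median 8 days; 12% deaths, counted as not recovered to day 20; no drug effect.

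**Direction, by formula.** A Weibull recovery hazard is proportional to t^(k−1).

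*Convention A: participants from enrollment, controls from admission.* On study day t the participant's hazard is that of hospital day t + L and the control's is that of day t. Leaving deaths aside, the null ratio is ((t + L)/t)^(k−1). With t = 8 and L = 2:
- k = 1.8: (10/8)^0.8 = 1.20, an apparent benefit.
- k = 1.0: (10/8)^0 = 1, neutral.
- k = 0.7: (10/8)^(−0.3) = 0.94, an apparent harm.

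*Convention B: both groups from admission, with no delayed entry.* Participants cannot recover before day L, but controls can. The ratio is 0 up to day L and 1 afterwards, so the average is below 1, against the drug.

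**Size, by null simulation.** One-sided false significance in %, 20 v 20, at lags of 1 / 2 / 3 days. Ranges are the spread across repeat runs.

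| Convention | Hazard | Error | Result |
|---|---|---|---|
| A | rising, k = 1.3 | false benefit | 3.6-3.9 / 4.6-4.7 / 5.7-6.5 |
| A | rising, k = 1.5 | false benefit | 4.3 / 6.5 / 9.0 |
| A | rising, k = 1.8 | false benefit | 5.3-5.6 / 9.4-9.9 / 14.2-14.4 |
| A | constant, k = 1.0 | false benefit | 2.3-2.7 at all lags |
| A | falling, k = 0.7 | false harm | 5.3-5.7 / 7.0-7.5 / 8.3-8.6 |
| B | rising, k = 1.8 | false harm | 2.9 / 3.3 / 4.7 |
| B | constant, k = 1.0 | false harm | 4.9-5.1 / 7.4-7.8 / 11.1-11.6 |
| B | falling, k = 0.7 | false harm | 8.2 / 13.4 / 19.4 |
| Aligned clocks, both at risk | all | either side | about 2.2-3.2 |

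The biased cells run from about 3% to just under 20%. This is not a ceiling: under convention A, with k = 2, a median of 10 days and no deaths, a 3-day lag gave 25.1% false benefit.

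**Survival.** Under convention A, with 10% or 20% mortality and several assumed death-time curves, the null mortality hazard ratio lay between 0.68 and 1.30. False significance was at most 6.3% for the drug and 5.5% against it at 20% mortality, and 3.0% and 3.6% at 10%.

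**Does covariate matching repair it?** This was tested with a prognostic covariate, a rising hazard, an assumed pool of 120 records and 3,000 trials per case. Matching on the covariate with controls counted from admission still gave false benefit of 3.8% and 10.7% at lags of 1 and 3 days. Matching on hospital day among those still at risk gave 1.7% and 2.1%.

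**The case against.** **The lag may be nil.** The inclusion criteria describe patients as they present, and same-day enrollment is possible. This stands: with no lag, the error is nominal. But nothing requires same-day enrollment, and Section 3 has patients recruited once in hospital.

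**A competent analyst would align the clocks.** Perhaps, but the plan does not say so, and the choice stays open after outcomes can be seen.

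**The comparison is not central.** Specific objectives 2 and 3 name no comparison, and two of the three primary outcomes are participant counts. This limits the reach of the point; it does not remove it.

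Three stronger readings are tempting, and the documents do not support them:

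- *That controls are to be counted from admission.* The time frame and the Section 2.2 rule do tie the 20 days to hospitalization, but both describe participants and neither sets an origin for controls. Read that way, they could equally put participants on an admission clock, which is convention B.
- *That the bias favours the drug.* That needs convention A and a rising recovery hazard. The documents establish neither.
- *That chart scoring will date control recovery late.* Telling category 3 from 4 in old charts needs a judgement, but early dating is as plausible as late. With clocks aligned, a quarter of controls dated one day late gives 2.9-3.6% false benefit; one day early gives about 2.8-3.5% false harm. Both are close to nominal.

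**Conclusion.** The specification gap is certain: the stated day-0 rules cannot be applied to the controls, and no rule puts them at risk on a comparable day. The resulting bias is conditional on enrollment after the admission day, and it can run either way. Its size cannot be known from the documents, which give no admission-to-enrollment lag, recovery curve or matching ratio. The 3-20% range rests wholly on the assumed lags, curves and 1:1 ratio; it shows what an unwritten choice could do and is not an estimate for this trial. It should be fixed because the repair is cheap and removes the dependence on those unknowns. That participants themselves have two clocks (enrollment and first dose) is minor.

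**What to change.** Add a paragraph to the Statistical Analysis Plan:

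1. Use the enrollment day as the single time zero for recovery and survival in the between-group tests.
2. For each participant, match on hospital day to registry patients who on that day are alive, hospitalized, unrecovered and eligible.
3. Build the propensity score from covariates recorded on or before that day.
4. Follow both groups for the same 20 days.
5. For the between-group test, score the ordinal scale in both groups from charts by one common written rule. Keep category 3 as the protocol defines it; limiting it to cases with an explicit chart statement would narrow the primary endpoint.
6. Add time to discharge alive as a sensitivity analysis.

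Treatment and enrollment do not change. The cost is more chart abstraction, some missing index-day values, and a smaller control pool. How much smaller cannot be calculated, because the size of the registry is not given.

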Scientific evidence proves the absence of short or long-term adverse effects of thymomodulin, obtaining significant results in the treatment of patients with immunological vulnerability in various respiratory pathologies (23). Taking this into account, it can be considered a promising alternative to combat the COVID-19 pandemic. The following sections will discuss the methodology of the clinical trial that will be used to evaluate its efficacy as a therapeutic option.

Hypothesis

Oral administration of thymic peptides (Unicahsina) is a safe and effective therapy for the management of patients with COVID-19 respiratory onsets.

General Objective

To demonstrate the therapeutic efficacy and safety of thymic peptides (Unicahsina) in patients with COVID-19 respiratory disease.

Specific objectives

- 1. To evaluate the safety of thymic peptides (Unicahsina) by monitoring adverse events using the Common Terminology Criteria for Adverse Events Version 5.0 (CTCAE v5.0) and side effects using the General Assessment of Side Effects (GASE).
- 2. Determine the time to participant recovery, according to a clinical ordinal progression scale.
- 3. To perform survival analysis in patients diagnosed with COVID-19 and treated with thymic peptides (Unicahsina).

SECTION 2 - DESCRIPTION OF THE POPULATION

2.1 Number of participants: 20 participants.

2.2 Describe the population:

Patients with diagnosis of COVID-19 confirmed by RT-qPCR testing, viral antigen detection or antibody detection plus associated symptomatology. The study will be performed in patients over 20 years of age without distinction of sex, race, religion, or socioeconomic status. Since the population under 20 years of age presents mostly mild or asymptomatic symptoms, with a mortality rate between 0% and 0.2%, it was decided to exclude this age range.

This research will involve elderly patients and those with comorbidities. The current COVID-19 pandemic has shown that this group of patients has the highest mortality rate, exposing the need to discover safe and effective therapies. Therefore, and given the innocuous profile that thymic peptides possess, we consider their use in this population.

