6.2 Describe how risks will be minimized

Monitoring of possible adverse reactions or side effects will occur after the administration of the drug. In case reactions that compromise the health of the participant appear, the drug will be suspended. If discomfort occurs when swallowing, a way will be sought to facilitate ingestion, fractionating the doses of the drug or its volume.

In case the placement of a nasogastric tube is required for the administration of the drug, it will be placed by trained personnel.

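### Version B primary outcome 2 is titled as treatment-related adverse events but defined as any Grade 3 or higher event, so the reported primary safety proportion depends on which reading is used

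*Combined protocol and SAP*

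**What the plan says.** Version B, Section 4.1, Primary outcome measures, item 2 has two parts. The title is "Number of participants with treatment related adverse events as assessed by" CTCAE v5.0, with a time frame of up to 20 days. The defining sentence begins "Number of participants who experience adverse events" and continues with a cut at Grade 3 or higher. The title names no grade, and the definition names no causal condition.

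Other places that might settle the matter:

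- **Specific objective 1:** "To evaluate the safety of thymic peptides (Unicahsina) by monitoring adverse events using the Common Terminology Criteria for Adverse Events Version 5.0". There is no relatedness qualifier.
- **Section 6.2:** "Monitoring of possible adverse reactions or side effects will occur after the administration of the drug". No causality categories, method or assessor are given.
- **Statistical Analysis Plan:** it has no safety paragraph. Counts are to be summarised as number and percentage.
- **Version A and the Summary of Changes:** Version A has the same wording for this outcome, and the Summary of Changes does not mention it.

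On data collection, the paragraph in Section 4.1 on administration says that information is gathered up to discharge or ICU referral, at which point administration stops.

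**The concern.** CTCAE grade measures severity and says nothing about cause. An outcome titled by cause and defined by severity can be counted in more than one way, and the choice could be made after the data are seen.

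The related-only count is the more fragile one. The trial is single-arm and open-label, so whoever attributes an event knows the patient received the product. The patients are hospitalized with Stage IIb COVID-19, where a severe event can readily be put down to the disease. The protocol also states a strong prior view: Section 1.3 says "Scientific evidence proves the absence of short or long-term adverse effects of thymomodulin", and Section 8.2 does not expect study-related injuries. With no attribution rule written down, the related-only count is open to bias towards showing no harm.

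What is at stake is the proportion reported for a primary outcome, and the support it gives to the hypothesis that the product is safe.

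**Working it through.** **1. Readings that fit the text**

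| Reading | Source | Restricted by cause? | Restricted to Grade 3+? |
|---|---|---|---|
| A. Any Grade 3+ event | Definition alone | No | Yes |
| B. Related Grade 3+ event | Title and definition combined | Yes | Yes |
| C. Related event of any grade | Title alone | Yes | No |

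B is a subset of A, so B can never exceed A. A and B agree only if every participant with a Grade 3+ event has at least one such event judged related, or if no Grade 3+ event occurs. C is not ordered against A.

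**2. Inputs**

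- Sample size: "2.1 Number of participants: 20 participants" (Version B, Section 2.1). I take n = 20 treated. Participants who withdraw are replaced, so the number treated could be larger.
- Event rates: none in the documents. The counts below are assumptions.
- The plan states no safety figure, so there is nothing to reproduce.

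**3. Exact (Clopper-Pearson) 95% intervals**

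For x of n, the lower limit is the 0.025 quantile of Beta(x, n − x + 1), and the upper limit is the 0.975 quantile of Beta(x + 1, n − x). For x = 0 the lower limit is 0 and the upper limit is 1 − 0.025^(1/20) = 0.168.

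| Assumed count | Proportion | Exact 95% CI |
|---|---|---|
| Reading B, 0/20 | 0% | 0 to 16.8% |
| Reading A, 2/20 | 10% | 1.2 to 31.7% |
| Reading A, 4/20 | 20% | 5.7 to 43.7% |
| Reading A, 6/20 | 30% | 11.9 to 54.3% |

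Each participant whose Grade 3+ events are all judged unrelated lowers the reported proportion by 1/20 = 5 percentage points. The overlap of these intervals does not make the gap harmless. A and B are two counts on the same patients, so their difference comes from the definition and not from sampling error.

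**4. Time frame**

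The outcome runs up to 20 days, but information stops at discharge or ICU referral. Under either reading, events after that point and before day 20 fall inside the stated time frame and outside the stated data collection. The two passages must be reconciled before the count has a defined observation period.

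**The case against.** The best defence is that a title and its description are normally read together: the title sets the class of event and the description adds the severity cut. That gives reading B and no contradiction. It is a reasonable reading, but the text does not state it, objective 1 does not share the restriction, and it leaves a primary outcome resting on a causality judgement the protocol never describes.

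Several stronger readings are tempting, and the documents do not support them:

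- **That the GASE outcome has the same fault.** Item 3 is titled "Number of participants with treatment related side effects as assessed by the General Assessment of Side Effects (GASE") and defined as "Number of participants who experience severe side effects as defined by the GASE". The term side effects already implies a treatment effect, so dropping the qualifier does not clearly widen the count.
- **That the protocol's own mortality figures size the gap.** If all of the 2.3% deaths fell in the 14% severe plus 5% critical, mortality there would be 2.3/19 = 12.1%, or 20 × 0.121 = 2.4 deaths. The documents never equate Stage IIb with those groups, and deaths are not the same as all Grade 3+ events. Deaths from any cause are in any case counted under overall survival, and invasive ventilation and death are categories 7 and 8 of the ordinal scale, so attribution would not remove them from those outcomes.
- **That a spurious safety benefit over the matched group would follow.** An assumed 0/20 related against 6/20 from all causes gives Fisher p = 0.020, but the plan does not specify a between-group safety comparison or a matching ratio.
- **That the protocol rules out harm altogether.** Section 6.1 concedes that unknown adverse effects in COVID-19 patients remain possible.

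**Conclusion.** The point holds for primary outcome 2. Title and definition disagree on whether cause matters, nothing else in Version B resolves it, and no causality method or assessor is given. The reported primary safety proportion therefore depends on an unstated choice.

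The size is illustrative only: 0% under reading B against 10% to 30% under reading A, on assumed counts in 20 patients. A reader might infer that the trial's safety conclusion would reverse. The documents do not support that, because they set no safety threshold, test or decision rule. What changes is the proportion reported and how far it can support an unqualified statement of safety. The outcome should be corrected, but this does not invalidate the trial.

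**What to change.** 1. Remove the relatedness qualifier from the title of primary outcome 2. Define the outcome as the number of participants with at least one CTCAE v5.0 Grade 3 or higher adverse event, regardless of attributed cause. This keeps the existing definition sentence.
2. State the period over which safety data are actually collected, and reconcile the 20-day time frame with the paragraph that gathers information only up to discharge or ICU referral.
3. Report investigator-attributed events as a secondary subset, naming the attribution method and the assessor.
4. Give exact 95% confidence intervals for both proportions, with the number treated as denominator.

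The GASE title can stay as it is. A table of laboratory-based events against the matched group is not needed: laboratory tests depend on hospital requirement and availability, so ascertainment could differ between groups.

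The cost is a change of wording, one added subset in the safety table, and a decision on the observation period. If that decision extends data collection beyond discharge or ICU referral, follow-up would have to change as well. The downside for the sponsor is a less favourable headline adverse event rate.
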